## 18.26 Immunogenicity

The following definitions based on [Shankar et.al. \(2014\)](#) will apply for this study:

- *Treatment induced ADA*: de novo development following administration of IMP (i.e., formation of ADA any time after the initial IMP administration for the first flare in a patient without pre-existing ADA).
- *Treatment boosted ADA*: Baseline ADA boosted to higher level following IMP administration (i.e., at any time after the initial IMP administration for the first flare the ADA titer is greater than the baseline titer by a factor of four).
- *Treatment-unaffected ADA*: Baseline ADA that does not change following IMP administration.
- *ADA positive patient*: A patient with at least one treatment-induced or treatment-boosted ADA positive sample at any time during the treatment or follow-up observation period.
- *ADA negative patient*: A patient without a treatment induced or treatment-boosted ADA positive sample during the treatment or follow-up observation period.
- *Transient ADA positive patient*: Patient with at least one treatment induced ADA positive sample after baseline and an ADA negative sample at the last sampling time point.
- *Persistent ADA positive patient*: Patient with treatment induced ADA-positive sample at 2 or more sequential sampling time points during the treatment including follow-up period and an ADA positive sample at the last sampling time point.
- *Off-treatment persistent ADA positive patient*: Patient remaining ADA positive after both anakinra drug and any transient ADA would be expected to have cleared (16 weeks after last dose within a flare). ADA detected after this period should be considered persistent off-treatment.

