## **9 General considerations for statistical analysis**

All statistical tests will be 2-sided and performed using a 5 % significance level, if not stated otherwise. Results will be presented as the point estimate for each treatment group, the estimated difference between groups, the associated 95 %, 2-sided confidence interval and p-value. P-values from statistical analyses will be presented to 3 decimal places with values below 0.001 displayed as <.001 and confidence intervals will be presented to one more decimal place than the raw data.

Continuous data will be summarized using descriptive statistics: n, mean, SD, median, minimum and maximum, unless otherwise stated. Minimum and maximum will be presented to the same number of decimal places as the raw data and mean, SD, standard error of the mean and median will be presented to one more decimal place than the raw data.

Categorical data will be summarized using counts and percentages. Percentages will be suppressed when the count is zero, however the category will still be displayed. The denominator for all percentages will be the number of patients within the treatment group for the population of interest, unless otherwise indicated. Percentages will be presented to one decimal place.

Statistical analyses will be performed using SAS software, Version 9.1 or later (SAS Institute Inc, Cary, North Carolina, United States).

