### **16.6.1 Presence of anti-drug antibodies**

The number and proportion of patients with presence of ADA (treatment induced, treatment boosted or treatment unaffected), NAb and cross-reactivity at baseline, Day 8, Day 15, Day 28 and Week 12 will be summarized for each flare.

For patients with presence of ADA, the ADA titers at baseline, Day 8, Day 15, Day 28 and Week 12 will be summarized by descriptive statistics for each flare. Depending on how the results are reported, ADA titers might be categorized as eg. low (<50), medium (>50 and <500) or high (>500).

The cumulative number and proportion of ADA positive and ADA negative subjects will also be summarized by flare over the study.

The number and proportion of transient ADA positive patients, persistent ADA positive patients and off-treatment persistent ADA positive patients will be summarized for the whole study,

The number of patients with occurrence of transient and persistent ADA during the study will be presented graphically.

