### **16.6.2 Anti-drug antibodies versus safety**

AEs and SAEs will be presented by ADA positive and ADA negative patients for the whole study period by SOC and PT. ADA positive patients will then be further categorized in:

1. Transient ADA positive patients.
2. Persistent ADA positive patients.

SAEs will be listed together with the ADA titer for the positive ADA sample taken closest before and after the start of the event.

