### **16.6.3 Anti-drug antibodies versus efficacy**

The mean pain intensity on VAS at each timepoint up to Day 8 will be presented by ADA presence and by NAb presence by descriptive statistics and in graphs as applicable. The presentations will be repeated for each subsequent flare. ADA presence will be defined as being ADA positive at least once at Day 1 or Day 8; no ADA presence will be defined as being negative at both Day 1 and Day 8. Undetermined ADA presence is defined as both assessments are missing or if one assessment is negative and the other is missing.

For subsequent flares, the ADA titer at Day 1 will be plotted against VAS at 72 hours.

For baseline, Day 8 and Day 15, CRP and SAA will be presented by ADA presence and by NAb presence. The presentations will be repeated for each subsequent flare. ADA presence will be defined as being ADA positive at least once at Day 1, Day 8 or Day 15; no ADA presence will be defined as being negative at both Day 1, Day 8 and Day 15. Undetermined ADA presence is defined as all assessments are missing or if 1 or 2 assessments are negative and the other assessments are missing.

For subsequent flares the ADA titer will be plotted against CRP and SAA at Day 1, Day 8 and Day 15.

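### SAP 18.26 lets a dosed patient with no post-dose ADA result count as ADA negative, and the default denominator keeps patients with cancelled visits in the visit-level ADA percentages

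*SAP*

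**What the plan says.** SAP 18.26 gives two patient-level definitions. ADA positive is "A patient with at least one treatment-induced or treatment-boosted ADA positive sample at any time during the treatment or follow-up observation period". ADA negative is "A patient without a treatment induced or treatment-boosted ADA positive sample during the treatment or follow-up observation period". Neither sets a minimum number of samples.

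Two displays use this split:

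- SAP 16.6.1: "The cumulative number and proportion of ADA positive and ADA negative subjects will also be summarized by flare over the study".
- SAP 16.6.2: "AEs and SAEs will be presented by ADA positive and ADA negative patients for the whole study period by SOC and PT". SAP Section 5 records that this patient-level split replaces the protocol's rule (9.3.4.11), which tied each event to the negative and positive assessments around it.

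SAP 16.6.3, on ADA against efficacy, does provide for missing samples. For VAS the rule is "Undetermined ADA presence is defined as both assessments are missing or if one assessment is negative and the other is missing". For CRP and SAA it is "Undetermined ADA presence is defined as all assessments are missing or if 1 or 2 assessments are negative and the other assessments are missing".

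On percentages, SAP Section 9 sets a default: "The denominator for all percentages will be the number of patients within the treatment group for the population of interest, unless otherwise indicated". Section 16.6.1 names no other denominator for its summaries at baseline, Day 8, Day 15, Day 28 and Week 12. Under SAP 8.3 the safety population needs only one dose of IMP. Under protocol 7.5.6.5 the first post-dose ADA sample is at Day 8, and the Day 28 and Week 12 samples are taken only if no subsequent flare has intervened.

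**The concern.** A missing result and a negative result are different findings, and the patient-level definition merges them. Someone who received IMP but gave no post-dose sample enters the incidence summary as evidence of no antibodies, and that person's adverse events are tabulated under ADA negative.

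The visit-level percentages have a related but separate problem. They do not use the 18.26 negative category. They report the presence of ADA, whether induced, boosted or unaffected. There the issue is the denominator: if it is the whole treatment group, a patient whose Day 28 or Week 12 visit was cancelled because a new flare was treated counts as not positive at that visit.

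Immunogenicity matters in this trial. Protocol 7.2.1 gives safety and immunogenicity as the primary purpose of the extension, and protocol 5.3 names allergic or injection-site reactions and reduced efficacy as possible results of ADA under intermittent dosing. No primary or secondary efficacy comparison depends on the definition.

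**Working it through.** **No plan figure to reproduce.** The documents give neither an expected ADA incidence nor a missing-sample rate. The only input from the plan is the planned number of anakinra patients, 53 + 53 = 106 (SAP Section 7). All other counts below are assumptions, shown over a range.

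**Step 1: the definitions side by side.** Positive means at least one induced or boosted positive sample, and negative means none. Every patient falls into exactly one class, so a not-evaluable patient cannot exist under 18.26. The undetermined rule in 16.6.3 does not fill the gap: it works by flare, concerns ADA presence rather than patient status, and applies only to the VAS, CRP and SAA displays. A dosed patient with a negative Day 1 sample and nothing afterwards is undetermined in the VAS display and ADA negative in the AE table.

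**Step 2: effect on cumulative incidence.** Let N be the patients dosed, k those with no post-dose result, m = k/N, and p the proportion positive among the N - k evaluable patients. Then

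reported proportion = p(N - k)/N = p(1 - m).

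The share of the ADA-negative group that has no post-dose result is k / (N - p(N - k)).

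With N = 106:

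| Unsampled, k | Reported if p = 10% | Reported if p = 30% | Unsampled share of negatives, p = 10% |
|---|---|---|---|
| 0 | 10.0% | 30.0% | 0% |
| 2 | 9.8% | 29.4% | 2.1% |
| 5 | 9.5% | 28.6% | 5.2% |
| 11 | 9.0% | 26.9% | 11.4% |
| 16 | 8.5% | 25.5% | 16.5% |

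For example, with k = 11, 10% x 95/106 = 9.0%. The reported proportion is lower than p whenever at least one dosed patient is unsampled and at least one patient is positive. Otherwise they are equal.

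**Step 3: effect on a visit-level percentage.** The same formula applies, with k now the patients without a Week 12 sample. Take p = 12.5% among those sampled:

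- 11 cancelled visits: 12.5% x 95/106 = 11.2%
- 21 cancelled visits: 12.5% x 85/106 = 10.0%
- 42 cancelled visits: 12.5% x 64/106 = 7.5% (8 positives among 64 sampled, against 8/106)

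This effect comes from the Section 9 default, not from 18.26.

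**The case against.** The strongest reply is that hardly anyone will be unsampled.

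- Protocol 7.3.3.1 keeps patients in follow-up after treatment stops.
- Under 7.3.3.2, a patient withdrawn from treatment for an IMP-related safety concern leaves the study only after Visit E. Other withdrawing patients are encouraged to complete assessments to that visit.
- ADA samples are also scheduled at Day 15, Day 28, Week 12 and every later treated flare, so missing Day 8 alone does not leave a patient without a result.

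All of this stands. A reader might infer that a patient who stops early after a reaction and misses Day 8 is thereby misfiled as ADA negative. The documents do not support that, because later samples are still due. The gap affects only a patient with no post-dose result at all.

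A reader might also infer that a post-dose positive with a missing baseline must be counted as negative, since neither induced nor boosted can be shown. The SAP is silent here, and such a patient could equally be coded as induced. This is an ambiguity. It should also be uncommon, because baseline blood is scheduled before the first dose.

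On the denominator, SAP 9.1 bases other secondary endpoints on observed data, and protocol 6.2.1 lists ADA occurrence as a secondary endpoint. SAP 3.3.3, however, files it under safety, while making the Day 28 and Week 12 assessments conditional on no subsequent flare. An observed-data denominator is therefore arguable. But Section 9 is the explicit rule for percentages and 16.6.1 does not depart from it, whereas SAP 14.3.1.10 states its own denominators for later-flare response, onset and resolution.

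Finally, the tables are descriptive, no hypothesis test is applied to adverse events, and individual listings are provided. This limits the consequence but does not supply the missing rule.

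**Conclusion.** The point holds in two parts. First, applied as written, 18.26 files unknown ADA status as negative in 16.6.1 and 16.6.2, while 16.6.3 keeps unknown status apart. Second, the Section 9 default, which 16.6.1 leaves in place, counts Day 28 and Week 12 visits cancelled by design as not positive.

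The patient-level effect is probably small, because follow-up continues after treatment stops. It is nil if every dosed patient has a post-dose result. The visit-level effect could be larger at Week 12, depending on how many visits are cancelled, which the documents do not say.

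A reader might take this to show that ADA incidence will certainly be understated, or that the AE comparison is biased in a particular direction. Neither follows. Understatement is relative to patients with a result and needs both an unsampled patient and a positive one. The direction of any bias in the AE comparison is unknown, because the true ADA status of the unsampled patients is unknown.

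The change is worth making because immunogenicity is a main aim of the extension and the correction is cheap.

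**What to change.** - **SAP 18.26:** require at least one evaluable post-dose sample, and none induced or boosted, for ADA negative. Add a not-evaluable/undetermined category for dosed patients with no evaluable post-dose sample. Place post-dose positives with a missing baseline in the same category, flagged as positive of undetermined origin so that the positive result stays visible.
- **SAP 16.6.2:** show this category separately from ADA positive and ADA negative in the AE and SAE tables.
- **SAP 16.6.1:** use patients with an ADA result at that visit and flare as the denominator for visit-level percentages, and print that number. Report the not-evaluable count beside the cumulative summary.

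The cost is SAP wording, one extra derived category with a flag, and small changes to table shells. No new data are needed. The change is best made before the first database lock, because the sponsor receives unblinded data after it (SAP 4.3). SAP 6.2 still allows a documented update before the final lock, but ADA status would then be redefined with treatment known.

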Visit 3 (Day 8): Blood sampling for central laboratory safety. Patient's assessment of pain intensity, patient's and physician's global assessment of response, physician's assessment of clinical signs, the patient's assessment of health related quality of life and health care resource utilization, assessments, immunogenicity assessments, inflammatory biomarkers and anakinra serum concentration assessments, vital signs, AEs and concomitant and rescue medication.

Visit 4 (Day 15): Patient's assessment of pain intensity, the patient's and physician's global assessment of response, the physician's assessment of clinical signs, the patient's assessment of health related quality of life and health care resource utilization.

Blood sampling for central laboratory safety assessments, immunogenicity assessments, inflammatory biomarkers and IL1ra/anakinra serum concentration assessments, physical examination and vital signs, AEs and concomitant and rescue medication.

Visit E (Day 28): Visit E will only be performed if no subsequent flare has occurred. Data will be collected on concomitant medication and adverse events. Blood will be collected for immunogenicity assessments and IL-1Ra/anakinra serum concentration assessments.

Visit 5 (Week 12): Visit 5 will only be performed if no subsequent flare has occurred. SAEs and outcomes of previously recorded AEs will be recorded and blood will be collected for immunogenicity assessments, inflammatory biomarkers and IL-1Ra/anakinra serum concentration assessments.

Follow up by telephone at every 12 weeks after Visit 5 of the latest flare (retention calls): A follow-up telephone call will be made to record outcomes of previously reported AEs and to encourage patient to remain in the study.

Subsequent flare(s):

Visits 1 to 5 (six visits; baseline, 72 hours, Day 8, Day 15, Day 28 and Week 12 after first IMP dose for subsequent flare): Assessments as described for Visits 1 to 5 above with the exception of informed consent, demographics (excluding weight) and randomization. Type of AEs to be collected will depend on time since last administration of IMP.

Follow-up by phone at 24 and 48 hours after first IMP dose for subsequent flare and at every 12 weeks after Visit 5 : Assessments as described for the first flare.

End of study:

End-of-study follow-up by phone will be performed either;

1. 52 weeks after randomization of the last patient in the study
or
2. 104 weeks after randomization of the individual patient

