7.4.6.2 Preparation and dosage

Anakinra and matching placebo

At each day of IMP administration period (Days 1 to 5), the anakinra and/or matching placebo will be given as two (2) s.c. injections of 0.67 mL solution in single-use prefilled syringes for s.c. injection.

30 minutes before injection, the prefilled syringes should be taken out from cold storage to equilibrate the injection solution with room temperature.

Triamcinolone and matching placebo

At Visit 1 of each flare, the triamcinolone or matching placebo will be given as one (1) i.m. 1 mL injection withdrawn with a syringe from a vial containing a 40 mg/mL solution. The vial should be shaken before use to ensure a uniform suspension. Prior to withdrawal, the suspension should be inspected for clumping or granular appearance (agglomeration). An agglomerated product results from exposure to freezing temperatures and should not be used.

In addition to the above instructions, a separate study drug handling manual will be provided. The manual will include working instructions for unblinded pharmacist/nurse responsible for removal of the triamcinolone/placebo vial caps if the caps differ in colour. The unblinded pharmacist/nurse must not be involved in the conduct of the study. The study monitor will inform the Investigator/Study Coordinator if an unblinded procedure is needed.

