7.5.1.8 Day 28, Visit E

Visit E will only be performed at Day 28±2 days if no subsequent flare has occurred.

Adverse events and concomitant medication will be recorded. Blood will be collected for, immunogenicity assessments and IL-1Ra/anakinra serum concentration assessments.

7.5.1.9 Week 12, Visit 5

Visit 5 will only be performed at Week 12±5 days if no subsequent flare has occurred.

SAEs and outcomes of previously recorded AEs will be recorded and blood will be collected for CRP and SAA, immunogenicity assessments, exploratory inflammatory biomarkers and IL-1Ra/anakinra serum concentration assessments.

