7.5.6.5 Anti-drug antibodies

Blood samples for determination of ADA will be collected before the first IMP administration, at Day 8, Day 15, Day 28 and Week 12 of each flare (at Day 28 and/or Week 12 only if no subsequent flare has occurred at an earlier time point). The date and time of blood collection will be recorded in the eCRF.

The sampling handling procedures, including the time of each blood collection, the time of placement of sera into frozen storage (at the end of the sample workup) and the date of transfer or shipment of the samples to the responsible analytical site will be documented in detail in the laboratory manual. The procedures and materials used, e.g. collection and storage tubes, will be described in the laboratory manual.

Serum samples to determine ADA will be analyzed by York Bioanalytical Solutions Limited using validated methods. This includes a bridging format immunoassay for screening of samples using a statistically defined cut-point for determination of an antibody positive result and a confirmatory assay with a statistically pre-defined confirmatory cut-point. Confirmed positive samples will be further analysed for antibody titers and for potential cross-reactivity with IL-1Ra that has been produced by a human cell line to achieve an endogenous-like glycosylation pattern to mimic natural human IL-1Ra.

Confirmed ADA positive samples will also be further analysed for the presence of neutralizing antibodies (NAb) at Euro Diagnostica with a validated method using an IL-1 responsive reporter gene cell line. Inhibition of the antagonistic effect of IL-1Ra on IL-1 mediated cell activation in the presence of an ADA positive serum sample will indicate the presence of NAb in the sample.

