### 3.3.3 Safety endpoints

The study has the following safety endpoints:

- Occurrence of AEs.
- Laboratory safety assessments.

- Vital signs .
- Occurrence of ADA against anakinra at Visit 1 (before IMP administration) and at Day 8, Day 15, Day 28 and Week 12 (the assessment at Day 28 and Week 12 will only be performed if no subsequent flare has occurred at that timepoint).

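### Off-treatment persistent ADA is defined at 16 weeks after the last dose, beyond the last scheduled sample of a flare, yet its proportion is taken over all patients rather than those who could be classified

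*SAP*

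**What the plan says.** SAP 18.26 defines an off-treatment persistent ADA positive patient as one who is still positive once both drug and transient antibody should have gone. It places that point at "16 weeks after last dose within a flare" and adds that "ADA detected after this period should be considered persistent off-treatment". SAP 16.6.1 plans the number and proportion of transient and persistent positives, and says that "off-treatment persistent ADA positive patients will be summarized for the whole study".

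The sampling schedule is the same in both documents. SAP 3.3.3 lists "Occurrence of ADA against anakinra at Visit 1 (before IMP administration) and at Day 8, Day 15, Day 28 and Week 12". Protocol 7.5.6.5 says that samples "will be collected before the first IMP administration, at Day 8, Day 15, Day 28 and Week 12 of each flare". The clock starts at the first dose: for later flares the protocol synopsis gives the visits as "baseline, 72 hours, Day 8, Day 15, Day 28 and Week 12 after first IMP dose for subsequent flare". Protocol 7.5.1.9 states that "Visit 5 will only be performed at Week 12±5 days if no subsequent flare has occurred".

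After Week 12, Protocol 7.5.1.10 and 7.5.1.11 provide for retention calls and an end-of-study call. Appendix 2 shows no blood draw at either.

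On denominators, SAP 9 makes the treatment group within the relevant population the default for every percentage unless a section says otherwise. Neither 16.6.1 nor 18.26 does.

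**The concern.** The definition asks for a sample that the schedule of a single flare never provides. A patient who has no further flare, or whose flares always return and are re-treated before 16 weeks have passed, cannot enter the category whatever the true antibody status. If such patients stay in the denominator, missing information is tabulated as a negative result.

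This matters because immunogenicity under intermittent dosing is a stated purpose of the extension. Protocol 7.2.1 says that the extension is mainly about safety and immunogenicity, and Protocol 5.1.4.2 says that repeated short courses had not been studied and might raise the risk of ADA. A low figure in this row could be taken as partial reassurance when some of it reflects absent samples.

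**Working it through.** The 16 weeks is a definition, so there is no computed figure in the plan to reproduce. The check is calendar arithmetic followed by a look at the denominator.

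**Step 1: inputs.**
- Threshold: 16 × 7 = 112 days after the last dose (SAP 18.26).
- Last s.c. dose: Day 5 for a full course (Protocol 7.4.6.2). Day 1 is tried as the extreme early stop.
- Last scheduled sample: Week 12 ±5 days (Protocol 7.5.1.9). The documents do not say whether this is Day 84 or Day 85, so both are used.

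**Step 2: days from last dose to last scheduled sample** = (Week 12 day + window) − last dose day.

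| Week 12 day | Last dose | Window −5 | Nominal | Window +5 | Short of 112 by |
|---|---|---|---|---|---|
| 84 | Day 5 | 74 | 79 | 84 | 28 to 38 |
| 85 | Day 5 | 75 | 80 | 85 | 27 to 37 |
| 84 | Day 1 | 78 | 83 | 88 | 24 to 34 |
| 85 | Day 1 | 79 | 84 | 89 | 23 to 33 |

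After a full course the range is 74 to 85 days: 74/7 = 10.6 weeks and 85/7 = 12.1 weeks. No convention, visit window or early stop closes the gap. The smallest shortfall is 112 − 89 = 23 days.

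**Step 3: who can be classified.** The threshold falls on Day 5 + 112 = Day 117 (Day 1 + 112 = Day 113 if dosing stopped after one day). The only ADA sample that can reach it is one taken at a later flare. Read as off treatment, that means the pre-dose Visit 1 sample of a flare starting at least 16 weeks after the previous last dose, because re-dosing restarts exposure. The SAP wording could also be stretched to samples taken during a later flare's follow-up. That reading still needs a later flare, and the patient is then no longer off treatment.

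**Step 4: effect of the denominator.** In one treatment group let N be all patients, A those with a qualifying sample, and X the positives among A.
- Reported as planned: X/N = (A/N) × (X/A).
- Shortfall against the rate among assessable patients: (X/A) × (1 − A/N).

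The shortfall is zero only if everyone is assessable or no assessable patient is positive. A/N depends on how often and when patients flare again. The documents do not project this, so A/N can lie anywhere between 0 and 1 and no size can be given.

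**Step 5: comparison with the rest of the SAP.** SAP 16.6.3 has an undetermined class when ADA samples are missing. SAP 14.3.1.10 bases the responder, onset and resolution percentages for later flares on patients who had that number of flares. Section 16.6.1 has neither device for this category.

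**The case against.** The strongest reply is that the extension exists to observe later flares. Protocol 7.2.1 keeps patients in the study until 52 weeks after the last randomization, up to 104 weeks each, so that a substantial number of later flares are treated, and every treated flare begins with a pre-dose ADA sample. The category can therefore be populated, and the sample before re-treatment is an informative one. That stands. It answers any suggestion that the category can never be met, but not the denominator problem.

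It is also fair that this is one descriptive row without a test or decision rule, and not an endpoint named in SAP 3.3.3. SAP 16.6.1 reports it beside persistent ADA, which needs no 16-week sample, and beside ADA, NAb and titers at each visit including Week 12. That limits how far a reader could be misled, and it stands too.

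A reader might go further and infer that most patients will be unassessable, or that the proportion will be close to zero and pass for proof that antibodies do not persist. The documents do not support this. Entry requires at least one flare in the previous 12 months and excludes only more than 12 in 6 months, so re-flare rates could vary widely.

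**Conclusion.** The point holds as a mismatch between a definition and its denominator. The last scheduled sample of a flare falls at least 27 days short of 16 weeks after a full course, and at least 23 days short in the extreme case. Classification therefore depends on a later flare visit at least 16 weeks after a last dose. As planned, the proportion counts patients without such a sample as not positive, and so understates the rate among assessable patients whenever that rate is above zero.

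The direction rests on two things: the SAP 9 default applies, since 16.6.1 states no other denominator, and not every patient has a qualifying sample. The amount cannot be derived from the documents. Nor is the rate among assessable patients an unbiased whole-study rate, since those patients are selected on when they flared.

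It may be tempting to move the definition to the Week 12 sample. The SAP's own reasoning speaks against that: 18.26 ties 16 weeks to the expected clearance of drug and transient antibody, and nothing in the documents supports clearance by about 10 weeks. It would also largely repeat the persistent category and the Week 12 table. The consequence is confined to one descriptive immunogenicity summary.

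**What to change.** Keep the 16-week definition in SAP 18.26 and amend 16.6.1 for this category:

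- Use as denominator only patients with an ADA sample at least 16 weeks after the last dose of a flare and before re-dosing.
- Report that number by treatment group.
- Report all other patients as undetermined, following the approach of SAP 16.6.3.
- Add a note that the assessable patients are selected on flare timing.

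The cost is a few lines of SAP text and one revised table. The category belongs to the whole-study analysis, and SAP 6.2 allows documented updates before the final database lock. No extra visit, sample or patient is needed. The downside is a smaller, selected denominator in one descriptive table.
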